## 8.6. Vital Signs, Physical Findings, and Other Observations Related to Safety

### 8.6.1. Vital Signs

Vital sign evaluation data will be presented by parameter as descriptive statistics for the change from baseline to each visit and shifts from baseline to each visit by treatment group and overall for subjects in the SfAS. Unscheduled visit and early termination visit data will not be mapped to scheduled visits per Section 7.1.2. Unscheduled visit and early termination visit data will be excluded from summary tables and included in listings. The analyses for shifts from baseline to each visit will use predefined clinically relevant categories to classify results into low, normal and high. Missing values will remain missing.

**Table 8-1 Vital Sign Categories for Clinical Relevance**

Vital Sign	Low	Normal	High
Systolic Blood Pressure (mmHg)	<90	90-120	>120
Diastolic Blood Pressure (mmHg)	<60	60-80	>80
Heart Rate (beats per minute)	<60	60-100	>100

Vital sign evaluation data will also be included in listings for subjects in the SfAS.

### 8.6.2. Physical Examinations

Baseline physical examination results of Normal, Abnormal and Not Done will be presented by body system as descriptive statistics by treatment group and overall for subjects in the SfAS. Missing values will remain missing.

Physical examination data will also be included in listings for subjects in the SfAS.

### 8.6.3. Ooscopic Examinations

Ooscopic examination data will be presented by visit for treated ears (time period after ear received any treatment) and untreated ears (time period before ear received any treatment), separately, as descriptive statistics for each classification of the examination by treatment group (actual treatment received) and overall for subjects in the SfAS, as described in Section 3. For unqualified ears that receive study treatment in error, ooscopic examination results will be mapped to untreated or treated ear(s) based on when study drug administration occurred in the unqualified ear, as described in Section 8.1. Because an ear is deemed treated after receiving any study treatment as described in Section 3, it is possible for both ears to be deemed treated at a visit. Unscheduled visit and early termination visit data will not be mapped to scheduled visits per Section 7.1.2.

Unscheduled visit and early termination visit data will be excluded from summary tables and included in listings. Missing values for each component will remain missing.

Otoscopic examinations will include the following classifications:

- Treated Ear: Right or Left. For subjects with a non-qualified ear that received study treatment, both ears will be classified as treated after the administration of study treatment in the non-qualified ear.
- External Inspection, Auricle and Meatus: Normal, Abnormal (Erythema, Cerumen, Otorrhea, Other).
- Internal Ear Examination:
  - Tympanic Membrane: Normal, Abnormal (Erythema, Bulging, Scarring, Granulation, Perforation, Other)
  - Tympanic Membrane – Perforation: Not Present, Present (Size of Perforation: Pinhole,  $\leq 25\%$  of the TM,  $> 25\%$  and  $\leq 50\%$  of the TM,  $> 50\%$  of the TM)
  - Middle Ear: Normal, Abnormal (Effusion, Otorrhea, Other)

The number and percentage of ears presenting with each otoscopic classification will be provided for treated ears (time period after ear received any treatment) and untreated ears (time period before ear received any treatment), separately, for each visit by treatment group (actual treatment received) and overall for subjects in the SfAS, as described in Section 3. The number and percentage of ears with shifts in their otoscopic classification from baseline to each visit will also be provided by ear (treated and untreated) for each treatment group (actual treatment received) and overall.

Otoscopic examination data, scheduled and unscheduled, will be presented in a data listing for subjects in the SfAS.

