| Urine Pregnancy Test (women of child bearing potential only) | X               | X b         | X b                        |                                    |                                     | X i       |
| Urine Drug Screen  | X a  |                        |                                       |                                    |                                     |                      |
| Safety Laboratory Assessments                                | X               |                        |                                       |                                    | X h                      | X i       |
| Blood sample for biomarker analysis                          |                 | X b         |                                       |                                    | X h                      |                      |
| Study Medication (FX-322 or placebo)                         |                 | X                      | X                                     |                                    |                                     |                      |
| Adverse Events   |                 | X c         | X b, c                     | X                                  | X                                   | X                    |

- a- See exclusion regarding positive drug tests
- b- Assessment performed prior to injection.
- c- Assessments performed after injection.
- d- Perform only at Day 15 visit.
- e- Visit windows: +/- 2 days for treatment visits, +/- 15 days for follow up visits.
- f- Subjects will be administered questionnaires over the phone or the internet depending on site's preference.
- g- Perform only at Day 60, 120, and 210 visits.
- h- Perform only at Day 210 visit.
- i- Perform at Investigator Discretion

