## 9 DISCONTINUATION AND LOST TO FOLLOW-UP

### 9.1 Discontinuation of Study Intervention

Discontinuation from FX-322 does not mean discontinuation from the study, and remaining study procedures should be completed as indicated by the study protocol. If a clinically significant finding is identified (including, but not limited to changes from baseline) after enrollment, the investigator or qualified designee will determine if any change in participant management is needed. Any new clinically relevant finding will be reported as an adverse event (AE).

The data to be collected at the time of study intervention discontinuation will include the following:

- All efforts will be made for the subject to complete all of the follow up visits.
- If the subject does not wish to continue the follow up period, all efforts will be made for the subject to complete all assessments collected at the last follow up visit (see Section 8.4.4).

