### **12.1.7 Otoscopy**

Microscopic otoscopy will be included to specifically record any abnormalities of the external ear canal, tympanic membrane and middle ear and will be performed at Screening, prior to injection on Day 1, 8, 15, and 21 and at the Day 60, 90, 150, and 210 visits.

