## 13 ADVERSE EVENTS

### Adverse Event Definition

An AE is defined as any untoward medical occurrence in a clinical study subject administered a medicinal product which does not necessarily have a causal relationship with this treatment. An AE can therefore be any unfavorable and unintended sign (including an abnormal laboratory finding), symptom, or disease temporally associated with the use of a medicinal (investigational) product, whether or not it is related to the medicinal (investigational) product. This includes an exacerbation of pre-existing conditions or events, intercurrent illnesses, drug interaction or the significant worsening of the indication under investigation that is not recorded elsewhere in the eCRF under specific efficacy assessments. Anticipated fluctuations of pre-existing conditions, including the disease under study that do not represent a clinically significant exacerbation or worsening need not be considered AEs.

It is the responsibility of the investigator to document all AEs that occur during the study. AEs will be elicited by asking the subject a nonleading question, for example, "Have you experienced any new or changed symptoms since we last asked/since your last visit?". AEs will be recorded from the time of the first treatment through the end of the follow up period. AEs should be reported on the appropriate page of the eCRF.

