### **Adverse Events of Special Interest (Audiometric and Otoloscopic)**

If any of the following criteria are met, the event will be recorded as an adverse event of special interest (AESI) per ASHA guidelines (ASHA 1994):

- Asymmetric loss of hearing greater than 20 dB at any one frequency in the treated ear compared to the Screening Visit.
- Asymmetric loss of hearing greater than 10 dB at two adjacent frequencies in the treated ear compared to the Screening Visit.
- Asymmetric loss of response at three consecutive test frequencies where responses were previously obtained in the treated ear compared to the Screening Visit.

For word recognition testing, a follow up visit score in the treated ear that falls below the lower limit of the 95% confidence interval of the baseline word recognition score will be considered an AESI (Thorton and Raffin 1978).

Additionally, if the subject experiences a perforation greater than 25% of the tympanic membrane in the treated ear this will be recorded as an AESI.

If any subjects in the study experience the same AESI, the Medical Monitor will discuss these with the Principal Investigators and each subject's condition will be discussed. The Medical Monitor, in consultation with the sponsor, will determine whether to proceed with any future doses if the subjects have not completed all 4 doses.

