**Table 7-1 Study Visit Windows**

Visit	Visit Number	Assessment/Day	Target Day	Target Window	Analysis Window a
Screening	1	-30 to 0	0	0	<0
Baseline/ Treatment	2a	1	1	1	1
Treatment	2b	8	8	6-10 (+/- 2 days)	2-11
	2c	15	15	13-17 (+/- 2 days)	12-17
	2d	21	21	19-23 (+/- 2 days)	18-24
Follow-up	3	30	30	25-45 (+/- 15 days)	25-45
	4	60	60	45-75 (+/- 15 days)	46-75
	5	90	90	75-105 (+/- 15 days)	76-105
	6	120	120	105-135 (+/- 15 days)	106-135
	7	150	150	135-165 (+/- 15 days)	136-165
	8	180	180	165-195 (+/- 15 days)	166-195
	9	210	210	195-225 (+/- 15 days)	196-225

aAnalysis windows are defined using the mid-points between each scheduled visit, and will be used to map early termination or unscheduled visit data to scheduled visits.

All scheduled visit data per Protocol Version 4.0, including assessments performed outside the target window, will be included in summary tables, figures, and listings. Scheduled visit data will be presented according to the nominal case report form (CRF) recorded visit and not re-mapped according to the analysis windows in [Table 7-1](#). Early termination visit and unscheduled visit efficacy data will be mapped to scheduled visits using the analysis windows in [Table 7-1](#). Early termination visit and unscheduled visit efficacy data will be included in tables and figures if no scheduled visit data is available for the nominal CRF recorded visit. If more than one unscheduled assessment (early termination or unscheduled) is performed within an analysis window, the assessment performed closest to the target day will be used. For safety tables and figures, early termination visit and unscheduled safety data will not be mapped to scheduled visits using analysis windows. Data for assessments that were planned to be performed at on-site study visits in Protocol Version 2.0 and were removed in Protocol Version 3.0 due to the switch to telephone visits will be excluded from tables and figures. All data, scheduled and unscheduled, will be included in listings.

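### Unscheduled and early-termination safety results are left out of the by-visit and shift tables with no any-post-baseline summary, so unless reported as an AE or AESI they appear only in listings

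*SAP*

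**What the plan says.** SAP 7.1.2 sets the general rule: "For safety tables and figures, early termination visit and unscheduled safety data will not be mapped to scheduled visits using analysis windows". Sections 8.5 (laboratory), 8.6.1 (vital signs), 8.6.3 (otoscopy), 8.6.4 (tympanometry) and 8.6.5 (C-SSRS) then each state: "Unscheduled visit and early termination visit data will be excluded from summary tables and included in listings". The tables in these sections are by visit, with shifts from baseline to each visit for all but the C-SSRS. None has a row for any post-baseline time.

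Efficacy data are handled differently in the same part of SAP 7.1.2: "Early termination visit and unscheduled visit efficacy data will be mapped to scheduled visits using the analysis windows in" Table 7-1, and they are used where the scheduled value is absent.

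The schedule sets how much this matters. Protocol 12.1.7 places otoscopy at Screening, then "prior to injection on Day 1, 8, 15, and 21 and at the Day 60, 90, 150, and 210 visits". Protocol 10.1.3 places the only tympanometry of the dosing period before the Day 15 injection. Protocol 10.1.4 makes Day 30 a phone contact. For post-baseline safety laboratory tests, the footnote in Protocol 8.1.2 reads "Perform only at Day 210 visit".

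**The concern.** Local and systemic safety is a primary objective (Protocol 7.1). Changes in otoscopy and tympanometry are named safety endpoints, listed separately from adverse events (Protocol 7.2), so these tables are the analysis of those endpoints and the AE table does not replace them.

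Unscheduled assessments are done at the investigator's discretion (Protocol 8.1.2). It is a reasonable inference, though the documents do not say so, that many would be prompted by a complaint. Exit assessments come from subjects who leave. The rule keeps both kinds of result out of every table built from these measurements. Safety data also get a less inclusive rule than efficacy data, and no reason is given. At stake is whether a reader comparing groups sees the minor ear findings and exit laboratory values that the trial collected.

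**Working it through.** The plan gives no figure to reproduce: safety is descriptive (Protocol 14.1.1), and 24 per group has no formal basis (Protocol 14.1.2). The check compares the exclusion rule with the schedule, and then with the other routes into a table.

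**Laboratory.** Scheduled samples are at Screening and Day 210 only. Protocol 8.4.4 encourages withdrawing subjects to complete the final evaluations, particularly those for safety. Such a sample is early-termination data, so SAP 8.5 lists it but does not tabulate it. The documents give no withdrawal rate (Protocol 8.4.1 expects all 96 to complete), so a range is assumed:
- 5%: 0.05 × 96 = 4.8, about 5 subjects
- 15%: 0.15 × 96 = 14.4, about 14 subjects

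This is an upper bound on what the rule removes. A subject who gives no exit sample has nothing to exclude.

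**Otoscopy after the fourth injection.** The Day 21 examination precedes the injection, and the next scheduled one is Day 60. Windows are ±2 days for dosing visits and ±15 days for follow-up.
- Nominal: 60 − 21 = 39 days
- Shortest: 45 − 23 = 22 days
- Longest within windows: 75 − 19 = 56 days

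Scheduled visits outside the window are still tabulated under their nominal visit (SAP 7.1.2), so the gap can be longer.

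**Tympanometry.** From Day 15 to Day 60 the nominal interval is 60 − 15 = 45 days (45 − 17 = 28 to 75 − 13 = 62). The Day 15 and Day 21 injections both follow the Day 15 test.

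**C-SSRS.** SAP 8.6.5 uses the Since Last Visit version at Days 60, 120 and 210. For a subject who stays in the study, the next scheduled administration covers the interval and is tabulated. The loss falls mainly on subjects with no later scheduled assessment.

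**Vital signs.** These are scheduled at Days 8, 15, 21, 60, 90, 150 and 210 (Protocol 8.1.2), so little is lost.

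**The AE route.** Protocol 9.1 requires any new clinically relevant finding to be reported as an AE. The AE definition in Protocol 13 covers "any unfavorable and unintended sign (including an abnormal laboratory finding), symptom, or disease". The AESI rule adds: "if the subject experiences a perforation greater than 25% of the tympanic membrane in the treated ear this will be recorded as an AESI". SAP 8.3 and 8.4.1 tabulate TEAEs and AESIs by subject, and SAP 8.3 also tabulates ear-related TEAEs by ear. None of these tables is tied to scheduled visits.

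**What remains outside every table.** Two kinds of result remain: a finding seen at an unscheduled visit, gone by the next scheduled one and not reported as an AE; and an exit value not reported as an AE. Examples are a pinhole perforation or one of up to 25% of the membrane, an effusion, a change of tympanogram type, or an out-of-range laboratory value.

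**Scale.** One omitted subject is 1/24 = 4.2 percentage points of a group. Protocol 6.2 cites perforations below 4% in a published steroid trial. At that ceiling, 0.04 × 96 = 3.84 events would be expected in the whole study, so a few omissions could empty the perforation row. Perforations reported as AEs would still count in the TEAE table.

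**The case against.** A reader might infer that symptom-prompted findings never reach a summary table. The documents do not support that: clinically relevant findings become AEs, perforations above 25% become AESIs, and both are tabulated whatever the visit type. An abnormality that persists to the next scheduled visit also enters the by-visit table. This part of the objection stands and sets the limit of the point.

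Other parts also stand. Otoscopy on Days 8, 15 and 21 examines the ear after injections one to three, so only the fourth lacks an early scheduled examination. That gap comes from the schedule; the exclusion matters only if an unscheduled examination takes place in it. Restricting by-visit tables to scheduled visits is defensible, because it avoids mixing protocol-timed and symptom-prompted examinations. The excluded data are listed in full, sorted by treatment group (SAP 3), for about 96 subjects.

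The AE route is nevertheless incomplete. It depends on the investigator judging a finding relevant. The AESI threshold leaves out the two smaller perforation categories that SAP 8.6.3 chose to record, and TEAE tables by preferred term are not specified to show size. Protocol 12.1.5 calls for interview and referral after a positive C-SSRS response but does not say that it is recorded as an AE. Listings give no counts by group, and the interim package in SAP 10 names otoscopy, tympanometry and C-SSRS outputs but no listings.

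**Conclusion.** The point holds in a limited form and is minor to moderate. The by-visit and shift tables omit unscheduled and early-termination safety results, and nothing summarises them over post-baseline time; unless reported as an AE or AESI, they appear only in listings. The effect is largest for laboratory data (at most about 5 to 14 of 96 subjects, on an assumed 5-15% withdrawal and an exit sample from every one of them) and for ear findings between the last injections and Day 60. It is small for the C-SSRS and smaller still for vital signs.

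The documents do not support a claim that the safety tables are shown to be biased toward no finding. The number of excluded examinations cannot be known from the plan, and the AE and AESI tables remain open to any finding that the investigator considers relevant.

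**What to change.** Keep the by-visit tables on scheduled visits. Add summaries by actual treatment group that take in every post-baseline assessment, whether scheduled, unscheduled or at early termination:
- Laboratory (8.5): shift from baseline to any low value and, separately, to any high value.
- Otoscopy (8.6.3): any abnormal finding in each classification and the largest perforation category, by ear.
- Tympanometry (8.6.4): any change from the baseline tympanogram type, by ear.
- C-SSRS (8.6.5): any post-baseline ideation or behaviour.
- Vital signs (8.6.1): any low and any high, optional.

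Defining each row this way avoids a single worst value, which has no clear meaning for tympanogram type or for measurements that can be abnormal in either direction. Include the otoscopy, tympanometry and C-SSRS rows in the interim outputs, limited to data through Day 90.

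The cost is a few extra tables from data already collected, with no change to visits or procedures. The drawback is that subjects with more examinations have more chances of a finding, so the rows should be labelled as reflecting unequal numbers of examinations.

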For assessments completed by ear for each subject, the unit of analysis will be the ear and treated and untreated ears will be summarized separately. An ear will be considered treated from the time it receives any dose, whether the qualifying ear or not. A subject's treated ear will be classified into an actual treatment group based on the actual number of FX-322 doses received in that ear. An ear will be considered not treated up until the time it receives any dose, whether the qualifying ear or not. Untreated ears will be classified in the Placebo group up until the time it receives any dose, after which the ear will be classified into an actual treatment group based on the actual number of FX-322 doses received in that ear. Pre-dosing measurements will be mapped to treated or untreated based on dosing at Day 1. Subjects with treatment received in the non-qualified ear may contribute more than 1 treated ear to SfAS analyses. In the event that any subject/ear combination(s) receive 3 FX-322 doses, separate reports for subject/ear combination(s) receiving 3 FX-322 doses will be created, as applicable. Subject/ear combination(s) receiving 3 FX-322 doses will be included in the FX-322 total ears column.

For example, a subject treated with FX-322 2x in the qualified ear at Days 1 and 8 and treated with FX-322 2x in the not qualified ear at Days 15 and 21 will be summarized as follows:

- a. For summaries by subject: This subject will be included in the FX-322 4x section of the table.
- b. For summaries by ear:
  - i. The qualified ear data will be reported at all visits in the FX-322 2x section of the table in the Treated column.
  - ii. The not qualified ear data up to and including Day 15 will be reported in the Placebo section of the table in the Untreated column.
  - iii. The not qualified ear data after Day 15 will be reported at visits after Day 15 in the FX-322 2x section of the table in the Treated column.

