#### 4. ANALYSIS SAMPLES

The following definitions will be used to derive the analysis sets for this study.

- Full Analysis Set

The Full Analysis Set is defined as all randomized subjects who receive at least one dose of study drug (regardless of whether a full dose was administered) in the qualified ear per the

randomized treatment schedule. Subjects will be analyzed according to their randomized treatment group, as described in Section 3. For assessments completed by ear for each subject, treated (qualified) and untreated (not qualified) ears will be summarized separately, as described in Section 3. The FAS will be used to explore efficacy.

- Per Protocol Analysis Set

The Per Protocol Analysis Set is defined as subjects receiving all four doses of study drug or placebo in the qualified ear to be treated per the randomization treatment schedule and without major protocol deviations that could interfere with interpretation of the results. These major protocol deviations will be identified prior to breaking the study blind for the IA. Protocol deviations that occur after unblinding for the IA will be evaluated for major/minor classification by the blinded medical and study team prior to breaking the study blind for the CSR. If different from the FAS, the PPAS may be used in additional sensitivity analyses for efficacy. PPAS subjects will be analyzed according to their randomized treatment group, as described in Section 3. For assessments completed by ear for each subject, treated (qualified) and untreated (not qualified) ears will be summarized separately, as described in Section 3.

- Safety Analysis Set

The Safety Analysis Set will include all subjects exposed to study drug or placebo in any ear and will be analyzed according to the actual treatment group regardless of their randomized treatment assignment, as described in Section 3. For safety assessments by subject, the total number of FX-322 received in any ear will be used to assign actual treatment group. For safety assessments completed by ear for each subject, treated and untreated ears will be summarized separately, as described in Section 3. The SfAS will be used for the analysis of safety.

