#### 8.6.4. Tympanometry

Tympanometry data will be presented by visit for treated ears (time period after ear received any treatment) and untreated ears (time period before ear received any treatment), separately, as descriptive statistics for each component of the tympanogram by treatment group (actual treatment received) and overall for subjects in the SfAS, as described in Section 3. For unqualified ears that receive study treatment in error, otoscopic examination results will be mapped to untreated or treated ear(s) based on when study drug administration occurred in the unqualified ear, as described in Section 8.1. Because an ear is deemed treated after receiving any study treatment as described in Section 3, it is possible for both ears to be deemed treated at a visit. Unscheduled visit and early termination visit data will not be mapped to scheduled visits per Section 7.1.2.

Unscheduled visit and early termination visit data will be excluded from summary tables and included in listings. Missing values for each component will remain missing.

Tympanogram data will include the following classifications:

- Treated Ear: Right or Left. For subjects with a non-qualified ear that received study treatment, both ears will be classified as treated after the administration of study treatment in the non-qualified ear.
- Type of Tympanogram (A, B, C)
- Type B – Volume (<2.0 mL, >=2.0 mL)
- Ear Canal Volume (mL)
- Peak Admittance (mL)
- Peak Pressure (daPa)

Treated Ear, Type of Tympanogram and Type B – Volume data will be summarized as the number and percentage of ears with each category and Ear Canal Volume, Peak Admittance and Peak Pressure will be summarized as continuous variables per Section 3. Summaries will be for treated ears (time period after ear received any treatment) and untreated ears (time period before ear received any treatment), separately, for each visit by treatment group (actual treatment received) and overall for subjects in the SfAS, as described in Section 3.

The number and percentage of ears with shifts from baseline to each visit in type and volume of tympanogram (A, B-small volume and/or normal, B-large volume, or C) will also be provided by ear (treated and untreated) for each treatment group (actual treatment received) and overall.

All tympanogram data, scheduled and unscheduled, will be presented in a data listing for subjects in the SfAS.

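### The treated-ear bullet in SAP 8.6.3 and 8.6.4 labels an uninjected qualified ear as treated if the wrong ear is injected first, against the ear-level rule in SAP 3 (minor)

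*SAP*

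**What the plan says.** **SAP 3, safety analyses by ear.** The rule works ear by ear and names the qualifying ear expressly: "An ear will be considered treated from the time it receives any dose, whether the qualifying ear or not", and conversely "An ear will be considered not treated up until the time it receives any dose, whether the qualifying ear or not". Group assignment is also by ear: "A subject's treated ear will be classified into an actual treatment group based on the actual number of FX-322 doses received in that ear". Until its first dose, an ear sits in the Placebo section as untreated.

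**SAP 8.6.3 and 8.6.4, tabulation sentences.** These refer to Section 3 and define the column by the ear's own exposure: "treated ears (time period after ear received any treatment". On the case of two treated ears, 8.6.3 says only that "it is possible for both ears to be deemed treated at a visit"; 8.6.4 says the same.

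**SAP 8.6.3 and 8.6.4, treated-ear bullet.** For a subject whose non-qualified ear received study treatment, "both ears will be classified as treated after the administration of study treatment in the non-qualified ear". There is no condition on the qualified ear.

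**SAP 4.** "The Safety Analysis Set will include all subjects exposed to study drug or placebo in any ear". A subject injected only in the wrong ear is therefore in these tables.

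**SAP 8.6.4, mapping sentence.** The tympanometry section says: "For unqualified ears that receive study treatment in error, otoscopic examination results will be mapped to untreated or treated ear(s" (the quotation stops at the bracket). It names the wrong examination.

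**The concern.** The bullet switches both ears to treated on an event in one of them. If the qualified ear has already been injected, that is correct. If it has not, an ear that no needle has entered is labelled treated, while SAP 3 keeps it untreated. A programmer could follow either text and produce a different table.

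Otoscopy and tympanometry are the two examinations that the protocol names, beside adverse events, as safety endpoints (Protocol 7.2). Both are also in the planned Day 90 interim output (SAP 10). An uninjected ear cannot show an injection injury, so counting it as treated adds to the denominator without exposure. The ear-level adverse event tables in SAP 8.3 follow Section 3 and have no such bullet, so the same ear could be untreated in one safety table and treated in another.

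**Working it through.** No figure stated in the plan depends on this rule. The check is to apply both rules to each possible order of injections and see where they differ.

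**Inputs**
- Four injections, on Days 1, 8, 15 and 21 (Protocol 8.1).
- Otoscopy before each injection, then at Days 60, 90, 150 and 210 (Protocol 12.1.7). That is 7 scheduled examinations after the first injection: Days 8, 15, 21, 60, 90, 150, 210.
- Tympanometry at Day 15, before injection, then at Days 60, 90, 150 and 210 (Protocol 10.1.3 and 12.1.8). That is 5 after the first injection.

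**Condition for conflict.** Write Q for an injection into the qualified ear and N for the non-qualified ear. The rules differ about the qualified ear at an examination when at least one N and no Q has gone before it.

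| Order | Otoscopy in conflict | Tympanometry in conflict |
|---|---|---|
| Q Q N N (the SAP 3 example) | none | none |
| N Q Q Q | Day 8 (1) | none |
| N N Q Q | Days 8, 15 (2) | Day 15 (1) |
| N N N Q | Days 8, 15, 21 (3) | Day 15 (1) |
| N N N N | all 7 | all 5 |

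**How many orders.** With all four doses given there are 2^4 = 16 orders, and 16 − 1 = 15 contain a wrong-ear injection. Otoscopy conflicts whenever the first injection is N: 2^3 = 8 of 15. Tympanometry conflicts whenever the first two are N: 2^2 = 4 of 15. In 1 of 15 the qualified ear is never injected. If doses may also be missed, 65 orders contain a wrong-ear injection; 40 conflict for otoscopy and 30 for tympanometry. These are counts of orders, not probabilities. If each ear is treated only from its own first dose, the count is 0.

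**Which column is affected.** SAP 3 groups a treated ear by the FX-322 doses received in that ear. Assume each visit's product follows the randomized schedule.
- N N N N: the qualified ear has 0 FX-322 doses in every arm, so the literal bullet puts it in Placebo/Treated instead of Placebo/Untreated.
- N Q Q Q: the qualified ear gets 0 FX-322 doses if randomized to placebo or 1x (Placebo column), 1 if randomized to 2x (FX-322 1x column), and 3 if randomized to 4x (separate reports and the FX-322 total under SAP 3).

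**Illustrative size.** The counts here are assumed. Take 24 treated ears in a column and add one uninjected ear without findings.
- 1 finding: 1/24 = 4.17% becomes 1/25 = 4.00%, a fall of 0.17 percentage points.
- 2 findings: 2/24 = 8.33% becomes 2/25 = 8.00%, a fall of 0.33 points.

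The only perforation rate in the protocol is under 4%, from a published trial of repeated intratympanic steroid injections (Protocol 6.2).

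**The case against.** The best defence is that the bullet does not govern the tables. It sits in a list of recorded items, beside the right/left field. It can be read as explaining why that field may hold both ears once a second ear is injected in addition to the qualified one. The tabulation sentences before and after it follow Section 3. This makes misclassification one possible programming outcome rather than what the plan as a whole prescribes, and that much stands. But the bullet does not state the assumption it needs, and it says how ears will be classified. The worked example in SAP 3 doses the qualified ear first, so it does not reveal the problem.

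Two stronger readings are tempting, and the documents support neither.
- *The effect always lowers the placebo rate and makes FX-322 look worse.* This follows only when the qualified ear has 0 FX-322 doses. A subject randomized to 2x with order N Q Q Q would dilute the FX-322 1x column instead.
- *SAP 8.6.4 leaves tympanometry without a mapping rule.* The mapping sentence does name the wrong examination. However, the section's own tabulation sentences apply the Section 3 rule to tympanometry, and SAP 8.1 gives the wrong-ear rule for safety analyses by ear in general. This is a copy-over slip.

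The stakes are also limited. Safety is analysed descriptively (Protocol 14.1.1). Perforations above 25% of the membrane are captured separately as adverse events of special interest and summarized by subject (Protocol 13, SAP 8.4.1). All otoscopy and tympanometry data are listed.

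**Conclusion.** The conflict is real but conditional, and minor. The bullet and SAP 3 classify the qualified ear differently only when the wrong ear is injected before the qualified ear's first dose, or is the only ear injected. The extent per subject runs from one otoscopy (N Q Q Q) to 7 otoscopies and 5 tympanograms (N N N N). The direction depends on the FX-322 doses the qualified ear receives.

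The plan does not say how many such subjects there are, so the effect on any reported rate cannot be computed. The percentages above rest on assumed counts and on the uninjected ear having no findings. Efficacy is untouched, because the FAS and PPAS define treated and untreated ears by qualification (SAP 3 and 4). A reader should not infer that the safety tables are wrong in general: in the order that SAP 3 illustrates, the two rules give the same result.

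**What to change.** In both 8.6.3 and 8.6.4, replace the sentence in the treated-ear bullet with: *Each ear is classified as treated from the time that ear first receives any dose and as untreated before then (Section 3); a qualified ear that has not been injected stays untreated, whatever was given to the other ear.*

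In the mapping sentence of 8.6.4, refer to tympanometry results instead of otoscopic ones.

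The cost is a few words of SAP text. No new data and no new analysis are needed; programs already written to Section 3 would not change.
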